3.4 CLINICAL MONITORING

3.4.1 Standard Clinical Laboratory Tests or Procedures

Tests may be performed +/- one day in week 1 and +/- 2 days in weeks 2-6. The following tests will be performed on the days listed below during all treatment cycles:

- **Routine chemistry panels** (acute care, hepatic and mineral) and LDH: MWF of each rhIL-15 and alemtuzumab treatment week. Except Week 3, when they will be done on Days 1, 2, 3 and 5.
- **CBC with differential:** MWF of each rhIL-15 and alemtuzumab treatment week. Except Week 3, when they will be done on Days 1, 2, 3 and 5.
- Serum Lipase and Amylase: Day 1 of each treatment week
- CMV PCR; Quantitative, Blood: Day 1 of each alemtuzumab treatment week
- **Troponin**: Day 1 of each treatment week.
- Other: ANA, RF, anti-thyroid antibody and thyroid panel (TSH \pm T4, if indicated): Day 1 of weeks 4 and 6.

3.4.2 Radiographic Evaluation and Laboratory Assessments for Clinical Responses

- All patients will have repeat baseline radiologic studies to assess marker lesions (measurable) and evaluable lesions (non-measurable) performed at the end of week 3 and week 6 for comparison to their pretreatment studies.
- Patients with evidence of a partial or complete response (RECIST criteria) **may** undergo a confirmatory scan that will be performed at least 4 weeks after the scan which first met the criteria for a clinical response to rhIL-15 plus alemtuzumab treatment.
- Appropriate patients will have tumor marker (IL-2R alpha) serum levels assessed at the time of their radiographic restaging to gain further insight into the potential efficacy of rhIL-15 plus alemtuzumab treatment.

3.4.3 Other Studies

Patients may have additional laboratory or radiological studies performed as clinically indicated,

Version Date: 09/24/2021

in particular if there were a suspicion of disease progression that would warrant an urgent therapeutic intervention.

3.4.4 Clinical Monitoring and Assessments

The following assessments will be performed on the days listed below during all treatment cycles:

- **Vital signs:** Including heart rate, blood pressure, respiration, temperature and oxygen saturation (SO2) by transcutaneous pulse oximeter.
 - o Within 2 hours prior to each IL-15 dose and 30-60 minutes after each IL-15 dose
 - O During the alemtuzumab treatment, the patient's vital signs (blood pressure, pulse, respirations, and temperature) should be monitored as follows:
 - During the first three doses alemtuzumab (and during subsequent doses until patient's vital signs remain stable during the preceding infusions), every 15 minutes (+/- 5 minutes) for first hour or until stable and then hourly (+/- 15 minutes) until the infusion is discontinued.
 - ➤ During subsequent doses (if patient's vital signs were stable during the first three doses): one hour after infusion starts (+/- 15 minutes); then every 4 hours (+/- 30 minutes) for the duration of the infusion, as long as patient is stable and has no signs/symptoms of reaction.
 - All non-treatment inpatient days: every 8 hours (+/- 2 hour); unless inpatient for social reasons, then VS once a day.
 - Outpatient non-treatment days: once per visit.
- Weight: Day 1 of each outpatient treatment week and every other day while an inpatient.
- Interval history and physical examination: Daily while inpatient, Day 1 (or within 5 days prior to day 1) of each outpatient treatment week and as dictated by adverse events on other outpatient treatment days.
- Documentation of performance status per Study Calendar (Section 3.5).
- Patients with cutaneous disease will have clinical photography performed to assess their skin disease at the end of week 3 and end of week 6, and a dermatology exam [mSWAT, **Appendix I**] performed at the end of week 6.

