1.2.4.4 Most advantageous rhIL-15 treatment schedule to be combined with alemtuzumab In the initial rhIL-15 IVB trial acute toxicities that began 2 to 2 ½ hours after the 30 minute infusion including decreased blood pressure requiring significant amounts of IV fluid support, temperature spikes not completely responsive to the addition of scheduled antipyretics and rigors likely related to intense cytokine production limited dose escalation and immune activation. These events seemed related to the high IL-15 C_{max} levels and were felt to be due to stimulation of cells that expressed only the IL-2/IL-15R beta and γc receptor. At roughly the same time these toxicities were being better understood through analyzing the data from the trial and data from the macaques' toxicology studies evaluating s.c. and CIV schedules. Data from the NHP showed a more favorable pharmacokinetic profile for the s.c. and CIV schedules that did not have extremely elevated early IL-15 levels and produced better lymphocytes expansions than the IVB schedule(76).

In the first in-human trial using Escherichia coli produced recombinant IL-15 (rhIL-15) evaluating patients with metastatic malignant melanoma or metastatic renal cell cancer, subjects were administered IV bolus injections of rhIL-15 at doses of 3.0, 1.0 and 0.3 mcg/kg per day for 12 consecutive days(77). A total of 18 patients were treated; 5 patients received 3.0 mcg/kg per day, 4 patients received 1.0 mcg/kg per day, and 9 patients received 0.3 mcg/kg per day for 12 consecutive days. Of these patients, 11 had a primary diagnosis of metastatic melanoma and 7 had a primary diagnosis of metastatic renal cell carcinoma.

The maximum tolerated dose was determined to be 0.3 mcg/kg per day. Dose limiting toxicities noted at the 1.0 mcg/kg per day and 3.0 mcg/kg per day doses included Grade 3 hypotension, thrombocytopenia and elevations of ALT and AST.

Flow cytometry of peripheral blood lymphocytes revealed an efflux of NK and memory CD8 T-cells from the circulating blood within 30 minutes upon IL-15 administration, followed by influx and hyperproliferation yielding a 10-fold expansion of NK cells that ultimately returned to baseline (**Figure 6**). Furthermore, there were significant increases in the gamma delta and CD8 memory T-cells.

Version Date: 09/24/2021

IL-15 by 12 Daily Bolus Infusions

[figure not shown]
[figure not shown]

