Figure 6: Effect of 12-daily bolus infusions of IL-15 on the fold change in the number of circulating diverse subsets of NK cells in patients with metastatic malignancy.

In this first in-human Phase I study there was no responses with stable disease as the best response. However, 5 patients manifested a decrease between 10 and 30 percent in their marker lesions and 2 patients had clearing of lung lesions.

1.2.4.5 A Phase I Study of Subcutaneous Recombinant Human IL-15 (rhIL-15) in Adults with Metastatic Cancer (NCT01727076)

Looking for an alternative dosing strategy, we went on to complete a Phase I trial of subcutaneous recombinant human IL-15 in cycles consisting of 5 daily injections of rhIL-15 given Monday-Friday for 2 weeks, then 2 weeks of observation with potential for additional cycles. Three patients each were enrolled in 0.25, 0.5, 1.0, and 2.0 mcg/kg/day dose levels and six patients were evaluated at 3.0 mcg/kg/day. Eighteen patients completed at least one cycle with one DLT at 3.0 mcg/kg/day and one serious adverse event, pancreatitis, at 2.0 mcg/kg/day (see Figure 7 for other AEs with s.c. IL-15). Flow-cytometry data indicated a consistent increase in the frequency of CD56bright CD3- negative NK cells peaking at day 15 (day 12 = last dose). The mean fold increase with 3 mcg/kg/day of IL-15 in circulating NK cell numbers peaked at 10.8-fold. The maximum fold increase in circulating CD8 + T cells was 3.3-fold. It was concluded that subcutaneous IL-15 was well tolerated and that the 2 mcg/kg/day dose level was the recommended phase II dose to be pursued in combination trials.(79)

[figure not shown]
Version Date: 09/24/2021

Figure 7: CITN11-02 Adverse Events

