3 STUDY IMPLEMENTATION

3.1 STUDY DESIGN

This is a single institution nonrandomized, IL-15 dose-escalation Phase I study evaluating the combination of s.c. rhIL-15 with alemtuzumab in patients with relapsed or refractory ATL, PTCL, T-PLL, or CTCL where both escalating doses of rhIL-15 and sequential administration of alemtuzumab will be administered.

rhIL-15 will be given as a subcutaneous (s.c.) injection once daily Monday-Friday for a total of 10 doses.

On Day 1 (or before if clinically indicated) of Week 3, patients will be admitted to the NIH Clinical Center inpatient unit for the alemtuzumab infusions. Patients may be discharged from the inpatient unit and treated in the outpatient clinic when their experience with the treatment indicates that the alemtuzumab can be given safely in an outpatient setting. **During week 3, all patients will receive standard initial (tachyphylaxis) dosing of alemtuzumab by 2-hour intravenous infusion:** Day $1 \rightarrow 3$ mg, Day $2 \rightarrow 10$ mg, and Day $3 \rightarrow 30$ mg and day $5 \rightarrow 30$ mg.

After completion of the initial dosing, alemtuzumab will be given to all dosing cohorts **during** weeks 4, 5 and 6 as the standard 30 mg on MWF schedule resulting in a total of 13 alemtuzumab treatments.

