5.1.1 Flow-Cytometry

Flow-Cytometry Studies will be done to assess for absolute numbers, percentages of lymphocyte sets, and T-cell subsets.

All FACS samples will be drawn in 10 mL lavender-top tubes and will be performed for the days listed below **during all treatment cycles.** FACS samples should be drawn before the day's dose of study drug. FACS panels will be performed by the [name] and [name] Laboratories for all time points listed. If the Immunology Section Laboratory ([name]'s Lab) is unable to perform the analysis on the specified days, this assessment maybe omitted or replaced with standard TBNK panel.

• Day 1 Pretreatment:

- Two 10 mL lavender top tubes drawn for cryopreservation, Clinical Support Laboratory, [name], [name], [name], [contact] or [contact].
- One 10 mL lavender top tube will be drawn and sent via routine collection routing to the Immunology Laboratory of the NIH Clinical Center 10/ for CD2, CD3, CD4, CD7, CD8, CD14, CD16, CD20, CD25, CD45RA, CD52, CD56, CD57,

Version Date: 09/24/2021

IL-2R/IL-15R beta (CD122), CD127 (IL-7R alpha), CD194, CD62L, IL-15R alpha.

- **Day 2:** Two 10 mL lavender top tubes will be drawn (+/- one hour) prior to administration of that day's rhIL-15 injection for FACS analysis and sent to the Clinical Support Laboratory for cryopreservation.
- Days 8, 26, 33 and 40: One 10 mL lavender top tube will be drawn with the routine blood draws on days 8 (+ 1 day), 26 (+/- 2 days), 33 (+/- 2 days), and 40 (+/- 2 days). Samples will be sent to the \ Clinical Center Immunology Lab as listed previously. Two 10 mL lavender top tubes will also be drawn for the [name] Lab (NIAID) at the same time and sent as specified above.
- 5.1.2 Inflammatory Markers and Cytokine Analysis
 - All samples will be drawn in 4 mL SST tubes at the times listed below.
 - O Week 1, Day 1 pre-therapy and 4 hours (+/- 15 mins), 8 hours (+/- 30 mins), 12 hours (+/- 30 mins) and 24 hours (+/- two hour) after first IL-15 administration
 - Week 3, Day 1 pre-therapy and 4 hours (+/- 15 min), 8 hours (+/- 30 mins), and 24 hours (+/-two hours) after first administration of alemtuzumab.
 - Samples will be sent via courier to:

Clinical Support Laboratory [name] [name] [name] [contact] or [contact])

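### Scheduled vital signs stop 60 minutes after each s.c. rhIL-15 dose, while the only reaction onset the protocol reports (IV bolus) is 2 to 2.5 hours, so later transient fever or hypotension may go unrecorded

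*Combined protocol and SAP*

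**What the plan says.** Route and schedule (Section 3.1): "rhIL-15 will be given as a subcutaneous (s.c.) injection once daily Monday-Friday for a total of 10 doses".

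Vital signs around each injection (Section 3.4.4): "Within 2 hours prior to each IL-15 dose and 30-60 minutes after each IL-15 dose". The vital-signs footnote to the study calendar only refers back to Section 3.4.4.

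Reaction timing (Section 1.2.4.4): "In the initial rhIL-15 IVB trial acute toxicities that began 2 to 2 ½ hours after the 30 minute infusion". The reactions named are falls in blood pressure needing substantial IV fluid, temperature spikes and rigors. The same section attributes them to peak exposure: "These events seemed related to the high IL-15 C_{max} levels". It describes the s.c. and continuous-infusion routes, from primate data, as "schedules that did not have extremely elevated early IL-15 levels".

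Timed blood draws after the first rhIL-15 dose (Section 5.1.2): "pre-therapy and 4 hours (+/- 15 mins), 8 hours (+/- 30 mins), 12 hours", and then 24 hours. No vital signs are tied to them.

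Other relevant text:
- The primary objective covers safety, toxicity profile and MTD (Section 1.1.1).
- Treatment may be inpatient or outpatient (Section 3.2).
- Vital signs, apart from baseline height and weight, are not entered in C3D (Section 6.1.2.2).
- A DLT is any related grade 3 or 4 toxicity in the first 6 weeks, with listed exceptions; fever and hypotension are not among them (Section 3.1.1).
- All adverse events are documented from the first study intervention (Section 6.1.1).

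**The concern.** The 30-60 minute window looks poorly matched to the one piece of timing evidence in the protocol. If s.c. reactions begin no earlier than the IV ones did, the only scheduled post-dose reading comes before them every time. The events are relevant ones. Grade 3 hypotension was among the dose-limiting toxicities of the IV trial (Section 1.2.4.4), and fever, chills and hypotension are listed as possibly related to rhIL-15 (Section 14.1.8).

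At stake is the completeness of the rhIL-15 toxicity profile. For an outpatient, a short fall in pressure or a temperature rise a few hours after the injection reaches the data only if someone notices it and it is recorded as an adverse event. Because C3D does not hold vital signs, it cannot be recovered later from the trial database.

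**Working it through.** **Inputs.** Post-dose reading: 30 to 60 minutes (Section 3.4.4). Reported IV-bolus onset: 2 to 2.5 hours, i.e. 120 to 150 minutes after the infusion (Section 1.2.4.4). Next scheduled reading: at most 2 hours before the following dose (Section 3.4.4). Doses: 10 (Section 3.1).

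**Step 1: reading against reported onset.**
- Smallest gap: 120 − 60 = 60 minutes.
- Largest gap: 150 − 30 = 120 minutes.

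The schedule is the same at every dose, so this applies to 10 of 10 doses.

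**Step 2: time to the next scheduled reading.** Assume doses 24 hours apart on weekdays and 72 hours apart from Friday to Monday.
- Consecutive weekdays: at least 24 − 1 − 2 = 21 hours.
- Week 1 Friday to week 2 Monday, outpatient: at least 72 − 1 − 2 = 69 hours.

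These are clock hours without a scheduled reading, not lost events. The weekend figure does not apply to inpatients, for whom Section 3.4.4 asks for readings every 8 hours on non-treatment days (once daily if admitted for social reasons).

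**Step 3: what the existing draws could add.** The 24-hour draw falls around the Day 2 pre-dose reading, so the new information would come from 4, 8 and 12 hours. The 4-hour draw (± 15 minutes) is at 225 to 255 minutes, which is 225 − 150 = 75 to 255 − 120 = 135 minutes after the IV onset. A very brief episode could still end before it. The draws cover 1 of 10 doses.

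**Step 4: could the DLT decision be affected?** First, the plan's own figure. Under its 3+3 rule, P(escalate) = (1−p)³ + 3p(1−p)² × (1−p)³, where p is the true DLT rate. For p = 10% to 60% this gives .906, .709, .494, .309, .172 and .082, matching the stated .91, .71, .49, .31, .17 and .08 (Section 10).

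Now suppose each DLT is independently missed with probability m, so that the rule sees p(1−m). The documents give no value for m; the columns are assumptions only.

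| True DLT rate | m = 0 | m = 10% | m = 25% | m = 50% |
|---|---|---|---|---|
| 30% | .49 | .56 | .65 | .81 |
| 50% | .17 | .23 | .35 | .60 |

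Missed DLTs would always raise the chance of escalating. How much depends wholly on m, and nothing in the documents shows that m is above zero.

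**The case against.** The strongest reply is the route. The 2 to 2.5 hour onset belongs to a 30-minute IV infusion, and the protocol links it to a peak level that s.c. dosing is meant to avoid. The earlier s.c. trial is described as well tolerated, with "one DLT at 3.0 mcg/kg/day and one serious adverse event, pancreatitis, at 2.0 mcg/kg/day" among 18 patients (Section 1.2.4.5), and no s.c. onset time is given. (Its adverse-event figure is not visible in the text available to me.) This stands: a reader might infer that 2 to 2.5 hours is the documented onset for this trial's route, and it is not. It does not rescue the window, however. A lower peak is a reason to expect milder reactions, not reactions confined to the first hour.

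Secondly, a reader might infer that the primary safety endpoint is under-recorded as a matter of fact. The documents do not support that. DLTs are any related grade 3 or 4 toxicity, adverse events are documented from the first dose, patients attend every weekday in weeks 1 and 2, and examinations are added as events dictate (Sections 3.1.1, 6.1.1, 3.4.4). Rigors, or hypotension needing fluids, are unlikely to pass unnoticed. What can be missed is mainly transient or asymptomatic change. That still matters, because the toxicity profile is itself part of the primary objective.

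Thirdly, a reader might contrast this with closer monitoring in the alemtuzumab weeks and infer a bias between phases. That does not hold either. The readings every 15 minutes and then hourly apply to the first three doses, or until the patient is stable. After that the schedule is one reading at 1 hour and then every 4 hours during the infusion, which for a 2-hour infusion is a single reading. This can apply to 10 of the 13 doses. The plan makes no between-phase comparison.

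**Conclusion.** The gap in the schedule is real. The single post-dose reading ends 60 to 120 minutes before the only rhIL-15 reaction onset the protocol reports, at all 10 doses, and the window is not justified. With outpatient dosing allowed and vital signs kept out of C3D, the recorded rates of transient fever and hypotension after rhIL-15 may be too low.

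This rests on one assumption: that s.c. onset is no earlier than IV onset. That is plausible from the description of early exposure in Section 1.2.4.4, but it is not documented. The size of any under-recording cannot be calculated. An effect on the DLT count or MTD is possible, and its direction would be toward more escalation, but neither its occurrence nor its size can be shown. I am confident about the mismatch in timing and much less so about its consequences.

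**What to change.** 1. Reconcile Section 3.4.4 with Section 1.2.4.4 for the s.c. route: either state why 30-60 minutes is informative for s.c. dosing or revise the text. Any further monitoring times are for the sponsor to choose; none is proposed here.
2. At the blood draws already scheduled after dose 1 in Section 5.1.2, record vital signs as safety data and capture abnormal values as adverse events. Because Section 6.1.2.2 keeps vital signs out of C3D, say there how these values reach the dataset. Section 6.1.2.1 already states when a laboratory abnormality counts as an adverse event; a matching statement for vital signs would serve.
3. State in the report that rhIL-15 fever and hypotension rates do not rest on the 30-60 minute reading alone, and how they were ascertained.

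The cost is a small amendment, a few extra readings on Day 1 when staff are already drawing blood, a modest change to data entry, and possibly slightly higher recorded event rates. Item 2 informs on one dose of ten and would not catch a very brief episode, so items 1 and 3 are needed as well. No sample size or decision rule changes.

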3.4.5 Follow-up Testing/Assessments

The following tests and assessments will be performed at every follow-up visit. Follow-up visits will occur every 60 days (\pm 7 days) for 6 months; then every 90 days (\pm 14 days) for up to 2 years after finishing treatment; and at the end of study visit (just prior to the patient being taken off study), if feasible:

- Vital signs
- Weight
- History and physical examination, including documentation of performance status
- ANA, RF, anti-thyroid antibody and thyroid panel (TSH \pm T4, if indicated)
- Routine chemistry panels (acute care, hepatic and mineral) and LDH
- CBC with differential

Version Date: 09/24/2021

- Serum lipase and amylase
- Radiographic evaluation, dermatology exam [mSWAT, **Appendix I**], Clinical Photography and laboratory assessments of disease status.

In addition to the tests listed above, the following tests will be done:

- CBC with differential **monthly** until CD4+ count >200 cells/μL
- FACS (standard TBNK panel) monthly until CD4+ cell count >200 cells/μL
- CMV PCR **monthly** for 2 months after alemtuzumab treatment is completed and CD4+ cell count >200 cells/ μ L

Abbreviated Title: SC IL-15 + alemtuzumab in ATL **Version Date:** 09/24/2021

3.5 STUDY CALENDAR

Test/Procedure	Screening ¹	² 1 VaU\əniləsa	І ЯээМ		Week 2		Меек 3		Week 4	L W22 11	2 1 /11	у Жеек	, , , , , , , , , , , , , , , , , , ,	у үзэм	Follow up ^{3, 24}	End of Study
Days		I	MWF T+Th		MWF T	T+Th	MWF	T+Th	MWF	T+Th	MWF	T+Th	MWF	T+Th		
rhIL-15			×	×	×	×										
Alemtuzumab							x ₅		x ₅		x ₅		x ₅			
Intrathecal prophylaxis							x ²⁷								x ²⁷	
Pathology confirmed, including CD52 positivity	×															
Flow Cytometry for lymphocyte sets & subsets; and CD52 10	×				x ¹⁰					x ¹⁰		x ¹⁰		x ¹⁰	X ^{10, 24}	
Flow cytometry for lymphocyte sets & subsets ([name] Lab) 11		x11	x ¹¹		x ¹¹					X ¹¹		x ¹¹		x11x		
History & Physical ⁶	×	×	x ₆		₉ x		₉ x		₉ x		₉ x		9X		×	×
Performance Score	Х	×	X ²⁰		\mathbf{x}^{20}				x ²⁰				\mathbf{x}^{20}		Х	×
Vital signs ⁷	X	X	x ⁷	x ⁷	x ⁷	x ⁷	\mathbf{x}^7	x ⁷	x ⁷		\mathbf{x}^7		\mathbf{x}^{7}		x ⁷	\mathbf{x}^7
Weight ⁷		X	x ⁷		x ⁷		x ⁷		x ⁷		x ⁷		x ⁷		x ⁷	x ⁷
Height		Х														
NIH Advance Directives Form ²⁵		×														
Imaging Studies (PET, CT, MRI or other as needed to document disease and response) ⁹	X	X					x ⁹						x ^{9,15}		x ⁹	₈ x
CBC with differential	х	×	×		×		×	×	x		X		×		x ²⁴	x
Acute Care, Hepatic and Mineral Panels and LDH	Х	X	х		Х		x	X	х		X		X		X	X
Serum lipase & amylase		×	\mathbf{x}^{20}		\mathbf{x}^{20}		X ²⁰		\mathbf{x}^{20}		\mathbf{x}^{20}		\mathbf{x}^{20}		X	X
Serum pregnancy test ⁸	X	₈ x														
Reticulocytes, Glucose-6 phosphate dehydrogenase (G-6PD)		X														
HIV 1&2, HTLV-1&2, Hepatitis B and C	×															

Abbreviated Title: SC IL-15 + alemtuzumab in ATL Version Date: 09/24/2021

Test/Procedure	Sereening ¹	aseline/Day 12	I AboW		Week 2		Меек 3		Week 4		У дээ УУ		9 ЯээМ	Follow up ^{3, 24}	⁴ ybutS to baA
Days		В	MWF 7	(+Th	MWF	+Th N	TWF 7	[+Th	MWF T+Th MWF T+Th MWF T+Th MWF T+Th MWF T+Th MWF T+Th	+Th M	WF T+	Ch MW	F T+Th		I
EKG	×														
Pulmonary function tests with DLCO	×														
Thyroid function tests		×							x ²¹			x ²¹		Х	×
Troponin		×	x ²⁰		x ²⁰		x ²⁰		x ²⁰		x ²⁰	x ²⁰			
Urinalysis		×													
ANA, RF and anti-thyroid antibody		×							x ²¹			x ²¹		\mathbf{x}^{21}	\mathbf{x}^{21}
CMV PCR; Quantitative, Blood		×					x ²²		x ²²		x ²²	x ²²		x ²⁴	
EBV PCR; Quantitative, Blood		×													
HLA typing (A, B, C, DR and DQ)		Х													
Reticulocyte Count		X													
Echocardiogram for LVEF	X														
Bone Marrow Biopsy		X													
Clonal T-cell receptor rearrangement by PCR ¹⁷		X													
Two Day and Six Day PBMC proliferation assay16		×													
Inflammatory Markers and Cytokine Analysis 12		X	\mathbf{x}^{12}				x ¹²								
Anti-IL-15 antibodies 13			x ¹³		x ¹³				x ¹³						
IL-2R alpha and MesoScale Discovery multiplex proinflammatory cytokines ^{14, 15}		Х	x ¹⁴		x ¹⁴		x ^{14,15}					x ¹⁵		x ¹⁵	
Special FACS and assay for ADCC		x ²³					x ²³	x ²³							
NK cell exhaustion studies		x ²⁶	x ²⁶		x ²⁶										
Skin biopsy if necessary to confirm the diagnosis of ATL or CTCL	X														
MRI scan of the brain and lumbar puncture for patients with neurological symptoms or signs ¹⁸	×														

Abbreviated Title: SC IL-15 + alemtuzumab in ATL Version Date: 09/24/2021

Test/Procedure	Sereening ¹	Baseline/Day 12		Меек 1	Week 2	7 433 44	E Apply	Меек 3	V 100M	Week 4	3 100/K	Week 5	Меек б		Follow up ^{3, 24}	End of Study ⁴
	Days	[_	T+Th	MWF	T+Th	MWF	T+Th	MWF	T+Th	MWF	T+Th	TWF T+Th MWF T+Th MWF T+Th MWF T+Th MWF T+Th MWF T+Th MWF	+Th		
Clinical Photography ¹⁹		×					x ₉						₆ x		x ₉	x ₉
Dermatology exam (mSWAT)19		×											X		x	×

NOTE: Any other tests should be performed as clinically indicated.

Screening evaluation must be performed within 28 days prior to study enrollment, unless otherwise noted.

² Baseline studies must be performed within 28 days prior to initiating treatment unless otherwise noted. It is not necessary to repeat tests that were done for screening if they were done within 28 days prior to initiating treatment. Day 1 studies must be done before that day's dose of study drug. It is not necessary to repeat tests that were done for baseline or screening if they were done within 28 days prior to initiating treatment.

of treatment visit will occur approximately 30 days after the last dose of study drug. If the patient cannot return to the Clinical Center for this visit, ³ Follow-up visits will occur every 60 days (\pm 7 days) for 6 months; then every 90 days (\pm 14 days) for up to 2 years after finishing treatment. End a request will be made to have a local physician or laboratory collect a CBC w diff and send the results. If this is not possible, patients may be assessed by telephone or email for symptoms.

⁴ End of study visit will occur just prior to the patient being taken off study, if feasible.

⁵ Alemtuzumab administration is described in Section 3.1. Please note: alemtuzumab administration is different for Week 3: It is administered at 3 mg on Day 1, 10 mg on Day 2, 30 mg on Day 3 and 30 mg on Day 5.

⁶ Complete H&P will be done on the Mondays prior to starting rhIL-15 treatment, upon admission to the hospital and for outpatient follow-up visits. A limited or focused interim history and physical exam will be performed daily while inpatient ⁷Vital signs: Including heart rate, blood pressure, respiration, temperature and oxygen saturation (SO2) by transcutaneous pulse oximeter will be measured and recorded as outlined in Section 3.4.4: Clinical Monitoring and Assessments.

⁸ Serum pregnancy test in women of childbearing potential, repeated within 3 days prior to starting the study drug.

there is confirmed or suspected disease involvement). At baseline one or more of the following studies may be done: CT, MRI, FDG-PET/ CT and insufficiency); other imaging may be substituted at the discretion of the investigator. Other body areas may be imaged if clinically indicated. MRI ⁹ At screening, CT scans of neck, chest, abdomen, and pelvis should be performed (with IV and PO contrast, unless patient is allergic or has renal of the brain is only required in patients with suspected involvement of CNS. At screening, a FDG-PET/CT torso (extremities to be included if

evaluable lesions (non-measurable) performed at the end of week 3 and end of week 6 for comparison to their pretreatment studies. FDG/ PET to or clinical photography. All patients will have repeat radiologic studies and Clinical Photography to assess marker lesions (measurable) and be done at Week 3 and After Cycle 6. Confirmatory scans may need to be done to confirm CR.

[name]. If the Immunology Section Laboratory is unable to perform this analysis on the specified days, this assessment maybe omitted or ¹⁰One 10 mL lavender-top tube will be drawn for FACS analysis. Samples will be sent to the Immunology Lab, NIH Clinical Center Bldg. 10/ replaced with standard TBNK panel. See Section 5.1.1 for collection times. ¹¹ Two 10 mL lavender-top tubes will be drawn and sent to Clinical Support Laboratory, Frederick to viably freeze PBMCs. See Section 5.1.1 for collection times. ¹²One 4 mL serum separator tube (SST) will be drawn for Inflammatory Markers and Cytokine Analysis. Samples will be sent to Clinical Support Laboratory, Frederick. See Section 5.1.2 for collection times.

¹³ One 4 mL serum separator tube (SST) will be drawn for anti-IL-15 antibodies and sent to Clinical Support Laboratory, Frederick. See Section **5.1.3** for collection times.

interferon gamma, IL-1 beta, TNF-alpha, IL-12, p70, IL-6, IL-10. Samples will be sent to Clinical Support Laboratory, Frederick. See Section ¹⁴ One 4 mL serum separator tube (SST) will be drawn for IL-2R alpha and MesoScale Discovery multiplex proinflammatory cytokines of 5.1.4 for collection times. 15 Patients will also have IL-2R alpha serum levels assessed at the time of their radiographic restaging to gain further insight into the potential efficacy of rhIL-15 plus alemtuzumab treatment. 16 To be collected from select patients, (this will be determined by physician PI or AI). Send four 10 mL sodium heparin green top tubes to [name] ([name]) for processing. The samples for the two-day proliferation assay will be sent to the lab at NCI/Leidos Biomedical Research, Inc.-Frederick, Clinical Support Laboratory for processing and analysis. The six-day proliferation assays will be performed in the Lymphoid Malignancies Branch Lab of [name]. The proliferation analyses are not a CLIA-certified (they are being collected for correlative studies). Every effort should be made to draw and send these tubes to [name] by 10 AM. ¹⁷Send one 10 mL sodium heparin green top tube for clonal T-cell receptor rearrangement by PCR to [name], Laboratory of Pathology, [name], [contact].

¹⁸ Patients with neurological symptoms or signs will undergo an MRI scan of the brain and lumbar puncture before enrollment.

¹⁹Patients with cutaneous disease will have clinical photography performed to assess their skin disease at the end of week 3 and end of week 6, and dermatology exam performed to assess the mSWAT score at the end of week 6.

²⁰ Day 1 of each treatment week.

²¹ Day 1 of week 4 and week 6.

²² Day 1 of each alemtuzumab treatment week.

²³ To be collected from select patients, (this will be determined by physician PI or AI). At Baseline, on Monday of Week 3 before administration of the first dose of alemtuzumab, and on Tuesday of Week 3 just prior to the second dose of alemtuzumab send up to four 10 mL sodium heparin green-top tubes to [name]., Lymphoid Malignancies Branch, in [name], and [contact].

²⁴ Additional tests to be done during follow-up period:

- CBC with differential **monthly** until CD4+ count >200 cells/µL.
- FACS (standard TBNK panel) monthly until CD4+ cell count >200 cells/µL.
- CMV PCR monthly for 2 months after alemtuzumab treatment is completed and CD4+ cell count >200 cells/ μ L.
- preferably at baseline but can be done at any time during the study as long as the capacity to do so is retained. The completion of the form is As indicated in Section 12.3, all subjects will be offered the opportunity to complete an NIH advance directives form. This should be done strongly recommended but is not required. 25.
- ²⁶ To be collected from select patients, (this will be determined by PI or AI). At Baseline, on Wednesday of Week 1 before IL-15 administration, and on Monday of Week 2 before IL-15 administration, send up to three 10 mL sodium heparin green-top tubes to Clinical Support Laboratory, Frederick, to viably freeze PBMCs. Tubes to be picked up by [name] ([name], [contact]) or courier.
- ²⁷ For patients with acute subtype ATL without prior CNS prophylaxis. Cytarabine 40 mg, methotrexate 15 mg, and hydrocortisone 50 mg administered intrathecally no earlier than Week 3 and every 6-8 weeks thereafter for up to three doses. See Section 3.2 for additional information.

Version Date: 09/24/2021

